### 3.6. Safety Endpoints

The primary and secondary safety endpoints are defined above in [Section 3.1](#) and [Section 3.2](#).

#### 3.6.1. Adverse Events

- The following risk period (RP) will be applied for TP1
  - For patients who entered TP1 and continued into TP2, RP is defined from date of 1st dose of TP1 to min (date of 1st dose of TP2 - 1, date of the last dose of TP1 + 35). This RP excluded AEs starting on the same day of 1st dose of TP2 or AEs starting on any day in TP2.
  - For patients who entered in TP1, permanently discontinued from study (and did not enter in TP2), RP is defined from date of 1st dose of TP1 to min (date of last contact, date of the last dose of TP1 + 35), where last contact date is min (date of discontinuation of study, date of data cut-off), if a subject dies, the death date will be the last contact date.
- The following risk period will be applied for TP2
  - For patients who entered TP2 and continued into TP3, RP is defined from date of 1st dose of TP2 to min (date of 1st dose of TP3 - 1, date of the last dose of TP2 + 35). This RP excludes AEs starting on the same day of 1st dose of TP3 or AEs starting on any day in TP3

- For patients who entered in TP2 and, directly entered in the Observation Period or permanently discontinued from study (and did not enter in TP3), RP is defined from date of 1st dose of TP2 to min (date of last contact, date of the last dose of TP2 + 35), where last contact date is min (date of discontinuation of study, date of data cut-off), if a subject dies, the death date will be the last contact date. This RP extends 35 days into the observation period.
- The following RP will be applied for Observation Period for patients who entered from TP2
  - For patients who entered the observation period from TP2, RP is defined from date of last dose + 1 to the last contact date, where the last contact date is min (date of discontinuation of study, date of data cut-off). If a subject dies, the death date will be the last contact date. This RP excludes AEs starting while on-drug.
- The following RP will be applied for TP3
  - For patients who entered in TP3, RP is defined from date of 1st dose in TP3 to min (last contact date, last dose date + 35) where last contact date is max (date of discontinuation of study, date of subject's last visit). In the case of an interim data cut, the last contact date is min (date of discontinuation of study, date of data cut-off). If a subject dies, the death date will be the last contact date. This RP includes AEs that occur within 35 days after the last dose
- The following RP will be applied for Observation Period for patients who entered from TP3
  - For patients who entered the observation period from TP3, RP is defined from date of last dose + 1 to last contact date, where last contact date is max (date of discontinuation of study, date of subject's last visit). In the case of an interim data cut, the last contact date is min (date of discontinuation of study, date of data cut-off). If a subject dies, the death date will be the last contact date. This RP excludes AEs starting while on-drug.
- Supplemental CSR1 will include summaries of TEAEs as described in [Table 4](#).
- Supplemental CSR2 will include summaries of TEAEs for the RP defined for TP3, and for the RP defined for the Observation period for patients who entered from TP3.

### 3.6.2. Laboratory Data

Below is a list of Laboratory Assessments to be performed at times specified in the schedule of activities in the protocol.

Hematology	Chemistry	Urinalysis	Other
Hemoglobin	BUN and creatinine	pH	At screening or Day 1 only: 
 
• FSH
 
• Pregnancy test (β-hCG)
 
• Hepatitis C antibody
 
• HIV
 
• HbA1C
 
• HbsAg
 
• HbcAb
 
• HbsAb
 
• HBVDNA
 
• HCVAb
 
• HCVRNA
 
• QFT-G test or T-Spot test
 
• Viral Screen
 
• Fasting Lipid profile
 

Hematocrit	Glucose	Glucose (qual)	
RBC count	Calcium	Protein (qual)	
%Reticulocytes	Sodium	Blood (qual)	
MCV	Potassium	Ketones	
MCH	Chloride	Nitrites	
Platelet count	Total CO 2 (bicarbonate)	Leukocyte esterase	
WBC count	AST, ALT	Urobilinogen	
Neutrophils	Total bilirubin	Urine bilirubin	
Eosinophils	Direct and Indirect bilirubin	Microscopy	
Monocytes	Alkaline phosphatase	Urine culture	
Basophils	Uric acid		
Lymphocytes	Albumin		
	Total protein		
	Creatine Kinase		
	Follow up testing for potential DILI cases		

### 3.6.3. Electrocardiogram (ECG)

ECG measurements will be collected at screening, at the end of placebo-controlled phase and at the end of active therapy extension phase.

### 3.6.4. Vital Signs, including Height and Weight

Vital sign measurements are pulse rate, blood pressure, respiratory rate, and oral, tympanic or axillary temperature. They will be performed at times specified in the schedule of activities in the protocol.

Height will be collected at screening and weight will be collected at both screening and baseline. Weight will be collected at the end of the placebo-controlled phase and at the end of the active therapy extension phase.

### 3.6.5. Physical Examinations

Complete physical examinations consist of assessments of general appearance; skin; head, eyes, ears, nose, and throat (HEENT); mouth, heart; lungs; abdomen; extremities; neurologic and auditory function; back; and lymph nodes. In addition, dermatological full body exam

must be performed by the investigator, sub-investigator or a qualified health professional per local guidelines. Dermatological examinations should also include visual inspection of the breasts and external genitalia.

Targeted physical examinations should include skin, heart, lung, and abdomen, neurologic and auditory function, and examination of body systems where there are symptom complaints by the participant.

Physical examinations will be performed at times specified in the schedule of activities in the protocol.

In addition, at the times specified in the protocol, all patients will have an audiological evaluation including BAEP by an audiologist and a neurological evaluation by a specialist.

#### 4. ANALYSIS SETS

For purposes of analysis, the following populations are defined:

Analysis Set	Description
Safety Analysis Set (SAS)	All participants taking at least 1 dose of study intervention. Participants will be analyzed according to the intervention they actually received.
Efficacy Analysis Set (EAS)	All randomized participants taking at least 1 dose of study intervention. Data will be summarized according to the intervention they were assigned.

#### 5. GENERAL METHODOLOGY AND CONVENTIONS

The primary analysis for this study will be conducted following the primary completion date (PCD) at Month 9 and after the Month 9 data are cleaned and locked.

##### 5.1. Hypotheses and Decision Rules

For the primary safety endpoint, there is no formal hypothesis testing. The analyses will focus on estimation. Summary statistics for each group with 95% confidence intervals will be provided.

No estimands will be defined since there is no formal statistical hypothesis testing for this study.

##### 5.2. General Methods

In the placebo-controlled period, the following continuous endpoints: (change from baseline in I-V interwave latency on BAEP, change from baseline in amplitude of wave V, and change from baseline in overall and AA SALT score, will be analyzed using the linear mixed -effects model with baseline, treatment group, visit, and treatment group by visit interaction as fixed effects, with an unstructured covariance matrix assumption, if there are convergence issues, a compound symmetry matrix will be used. The Kenward-Roger degrees of freedom approximation will be used. For participants who switch to the active therapy extension phase at Month 6, only their data through Month 6 will be included in the analysis of the placebo-controlled period. Descriptive statistics based on observed data will also be provided. For TP2 and TP3, descriptive statistics will be presented.

For the binary endpoint PGI-C response, in the placebo-controlled phase, number and percentage of responders with 95% confidence interval (based on Clopper-Pearson method) by treatment group, and treatment difference with 95% confidence intervals (based on Chan and Zhang's exact method) will be presented. Participants who discontinue from the study for any reason or who switch to active therapy extension phase before Month 9 will be considered as non-responders. Number and percentage based on observed data will also be provided. For TP2 and TP3, number and percentage of responders with 95% confidence interval (based on Clopper-Pearson method) will be presented based on observed data.

For all other data, descriptive summary statistics such as number and percentage will be presented for binary variables, and number, mean, standard deviation (or standard error of the mean), median, minimum, and maximum will be presented for continuous variables.

### 5.3. Methods to Manage Missing Data

- For the PCD CSR
  - For change from baseline in I-V interwave latency on BAEP, change from baseline in amplitude of wave V, and change from baseline in overall and AA SALT score during the placebo-controlled phase, the missing values will be handled in a linear mixed-effects model (Section 5.2).
  - For the PGIC response, participants who discontinue from the study for any reason or who switch to active therapy extension phase before Month 9 will be considered as non-responders at Month 9.
- For supplemental CSR 1 and CSR 2
  - All efficacy data will be summarized based on observed data. Missing data will not be imputed.

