7.1.1.1. Observation Period

Participants will be asked to remain in the study after the Follow-up visit without study intervention. The Period during which participants are in the study after having permanently discontinued study intervention is referred to as the Observation Period. During this period participants will continue to comply with study visit schedules for approximately 2 years or until study end, whichever occurs first. At visits during the Observation Period, only the SALT, PGI-C, and concomitant medications/treatments will be collected at the visits specified in the applicable SoAs in Section 1.3.2; AE and SAE reporting will follow the guidelines in Section 8.3.

Participants will complete the final visit in the Observation Period approximately 2 years after the last dose of study intervention or at study end whichever occurs first as follows:

- at the protocol-scheduled visit 24 months after the last dose of study intervention, OR
- at the next scheduled visit after the 24-month time point (if no scheduled visit falls at the 24-month time point), OR
- at study end.

For example, if the last dose of study intervention occurs around the time of Month 22E then the final visit in the Observation Period would be conducted at Month 51E (ie, the next closest scheduled visit occurring 24 months after Month 22).

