**Table 3. Groups**

Period	Groups
Placebo-controlled phase (TP1)	
 
• Ritlecitinib 200/50 mg QD
 
• Placebo
 

Active therapy extension phase (TP2)	
 
• Ext Ritlecitinib 50 mg QD
 
• Ext Ritlecitinib 200/50mg QD
 

Overall (TP1+TP2)	
 
• Ritlecitinib 200/50/50 mg QD
 
• Any Ritlecitinib
 
• Any Ritlecitinib + Placebo (Total)
 

For tables summarizing data by visit (such as BAEP, skin punch biopsy endpoints and efficacy endpoints), which only include data from TP1 in the PCD-CSR, the following groups will be summarized:

- Ritlecitinib 200/50 mg QD
- Placebo

For other tables such as dispositions, demographic and baseline characteristics, medical history, primary diagnosis, prior medications and compliance the groups to be summarized will be:

- Ritlecitinib 200/50 mg QD
- Placebo → Ritlecitinib 200/50 mg QD.

## 8.2. Supplemental CSR 1

The supplemental CSR 1 will be prepared after the last participant completes the 4-week follow-up visit, or the Month 15E visit (TP2) if the last participant is enrolled in TP3, whichever is later. This CSR will include:

- Efficacy through Month 15E (TP1+TP2). Efficacy data from participants while they are on the Observation Period will not be included in the summaries of efficacy. Instead, listings and plots may be provided.
- All safety data collected through the cut-off date for this CSR (including the Follow-up Period and the Observation Period).

For summaries in this CSR, the groups will be the following:

- For duration of treatment, concomitant medication, lab abnormality, lab values meeting discontinuation criteria, vital signs/QTcF values meeting pre-specified criteria and AE tables.

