**Table 4. Groups**

Period	Groups
Placebo-controlled phase (TP1)	
 
• Ritlecitinib 200/50 mg QD
 
• Placebo
 

Active therapy extension phase (TP2)	
 
• Ext Ritlecitinib 50 mg QD
 
• Ext Ritlecitinib 200/50mg QD
 

Overall (TP1+TP2+TP3+Observation period)	
 
• Ritlecitinib 200/50/50 mg QD
 
• Any Ritlecitinib
 
• Any Ritlecitinib + Placebo (Total)
 

- For all the other tables, groups will be:
  - Ritlecitinib 200/50/50 mg QD
  - Placebo → Ritlecitinib 200/50 mg QD.

### 8.3. Supplemental CSR 2

The supplemental CSR 2 will be focused on safety and efficacy data from TP3 and will be prepared after the last participant completes the last visit or discontinues from the study.

- Disposition date of TP2 (or of 4 weeks follow-up period if participants didn't enter TP3) will be used to identify records in TP2 and TP3.
- All safety data in TP3, regardless of whether participants are in the Observation Period or not, will be included in summary tables.
- Only one group “All participants” including all participants will be used in all summaries.
- Efficacy data of participants while in the Observation Period will not be included in summary tables that present TP3 data by visit. Instead, listings and plots may be provided.

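### TP2 and TP3 efficacy summaries leave out the SALT and PGI-C values collected after permanent discontinuation, so the long-term response rates describe participants remaining on drug rather than all who entered each period

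*SAP*

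**What the plan says.** **Missing data.** For both supplemental reports SAP 5.3 states: "All efficacy data will be summarized based on observed data. Missing data will not be imputed". SAP 5.2 and 6.3.2 apply this to PGI-C as number, percentage and Clopper-Pearson interval on observed data. Protocol 9.4.2 also specifies observed data for TP2 and TP3.

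**What is collected after stopping.** Protocol 7.1.1.1 asks participants who permanently stop drug to remain in the study. It says: "At visits during the Observation Period, only the SALT, PGI-C, and concomitant medications/treatments will be collected". It adds: "Participants will complete the final visit in the Observation Period approximately 2 years after the last dose of study intervention", or at study end if that comes first.

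**What is done with it.** SAP 8.2 (CSR 1): "Efficacy data from participants while they are on the Observation Period will not be included in the summaries of efficacy". SAP 8.3 (CSR 2): "Efficacy data of participants while in the Observation Period will not be included in summary tables that present TP3 data by visit". In both places listings and plots are optional. For safety, SAP 8.3 does the opposite: "All safety data in TP3, regardless of whether participants are in the Observation Period or not, will be included in summary tables".

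**TP1, for contrast.** SAP 5.2 says of PGI-C: "Participants who discontinue from the study for any reason or who switch to active therapy extension phase before Month 9 will be considered as non-responders". It also provides the observed-data number and percentage beside that analysis.

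**A conflicting passage.** SAP Appendix 1 names the Observation Period as a source of data for deriving TP3 analysis visits.

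**The concern.** The observed-data sentence in SAP 5.3 excludes nobody by itself, because an off-drug SALT or PGI-C value is still an observed value. The exclusion comes from SAP 8.2 and 8.3. Taken together, the three provisions remove permanent stoppers from each by-visit efficacy table once their last usable value has passed. No planned TP2 or TP3 summary puts them back.

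This matters because Protocol 2.3 says the study will extend the benefit-risk analysis to as much as five years, and the TP3 objectives speak of long-term response. A rate among those who remain answers a narrower question: how people are doing if they are still taking the drug. If non-responders stop more often than responders, that rate will exceed the rate among all who started the period, and a rise over visits could reflect who has left rather than further regrowth.

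The information needed to check this is collected on purpose. SALT and PGI-C are the only efficacy measures taken in the Observation Period, yet the SAP commits to no efficacy table that uses them.

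**Working it through.** **The plan's own figure.** The only design figure is the 0.07 ms half-width for the primary endpoint (SAP, Sample Size Determination). It reproduces: 1.96 × 0.2 / √30 = 0.0716 ms, or 0.0747 ms with a t quantile on 29 degrees of freedom. It does not bear on this point, and no figure is given for TP2 or TP3 efficacy.

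**Who contributes to a TP2 or TP3 visit.** Read together, the provisions give:

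- On drug with a value: counted.
- At Early Termination: can be counted. Protocol 1.3.3 collects SALT and PGI-C there, and the value can fall in an analysis window. SAP Appendix 1 uses TP2 data until the end of follow-up or the first TP3 dose.
- In the Observation Period: not counted in CSR 1 efficacy summaries (SAP 8.2) or TP3 by-visit tables (SAP 8.3). Appendix 1 points the other way for TP3.
- Missing: not counted and not imputed (SAP 5.3).

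**Relation between the two rates.** Let d be the share of entrants who permanently stop for non-administrative reasons, p the response rate among stayers, and q the response rate among stoppers.

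- Planned rate = p
- Rate over all who entered = p(1 − d) + qd
- Gap = d(p − q)

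With stoppers counted as non-responders (q = 0), the all-entered rate is p(1 − d). The sign of the gap depends only on whether p exceeds q.

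**Illustration.** Assumptions: 30 enter TP2 per initial group (the planned group size, so an upper limit if all randomized enter), about 70% of stayers respond, 10% to 40% stop, and there are no administrative exits. Counts are rounded to whole participants. Gaps are in percentage points, from unrounded proportions.

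| Stop | Stayers (planned rate) | All entered, q = 0 | Gap, q = 0 | Gap, q about 20% | Gap, q about 50% |
|---|---|---|---|---|---|
| 3 | 19/27 = 70.4% | 19/30 = 63.3% | 7.0 | 3.7 (20/30) | 0.4 (21/30) |
| 6 | 17/24 = 70.8% | 17/30 = 56.7% | 14.2 | 10.8 (18/30) | 4.2 (20/30) |
| 9 | 15/21 = 71.4% | 15/30 = 50.0% | 21.4 | 14.8 (17/30) | 8.1 (19/30) |
| 12 | 13/18 = 72.2% | 13/30 = 43.3% | 28.9 | 22.2 (15/30) | 8.9 (19/30) |

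For scale, the Clopper-Pearson 95% intervals in the second row are 48.9% to 87.4% for 17/24 and 37.4% to 74.5% for 17/30.

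The gap can change sign. With 14/27 = 51.9% of stayers responding and 2 of 3 stoppers responding, the all-entered rate is 16/30 = 53.3%, which is 1.5 points above the planned rate.

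**CSR 2.** SAP 8.3 uses one pooled group of all participants, so a split by initial arm does not apply there. With 60 entrants as an upper limit, 20% stopping gives 34/48 = 70.8% against 34/60 = 56.7%, and 40% stopping gives 25/36 = 69.4% against 25/60 = 41.7%. Actual TP3 entry will be lower if some participants decline or live where the product is on the market.

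**The case against.** The strongest reply is that this is a legitimate on-treatment summary. This is a Phase 2a safety study with no hypothesis tests, and the endpoints are descriptive: secondary in TP2 and exploratory in TP3. Keeping off-drug hair loss separate from on-drug response is defensible. Disposition is summarized (SAP 6.6.2) and the tables show counts, so a shrinking denominator will be visible. All of that stands. It limits the weight of the point, but it does not supply the rate among all who entered.

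Several stronger readings are tempting, and the documents do not support them:

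- *Response will drift upward as failures leave.* Protocol 7.1.1 describes permanent discontinuation as rare and gives safety-type reasons, and Protocol 10.7.2 lists no lack-of-efficacy criterion. Participants may also leave by choice, but no rates or reasons are given.
- *The rate jumps at the TP1/TP2 boundary because the rule changes.* Only the non-responder series ends there. TP1 also reports observed data, so an observed-case series runs through both periods. A change is also expected because the placebo group starts active drug.
- *Only people still on drug count, and every output excludes the rest.* An Early Termination value can still count, the SAP 8.3 restriction covers by-visit summary tables, and listings and plots remain possible.
- *All randomized participants are the right denominator at Month 51E.* That would count people who never entered TP3, or who left because the product reached the market or the sponsor closed the study in their country, as treatment failures.

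Off-drug data may also be sparse. Participants are only asked to stay, and Protocol 10.7.2 speaks of withdrawing from the study those who meet its criteria, whereas 7.1.1 says stopping drug is not withdrawal from the study. Those two passages need to be reconciled.

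**Conclusion.** The point holds as a matter of what the tables will describe. Under SAP 5.3, 8.2 and 8.3, TP2 and TP3 response rates refer to participants remaining on drug, plus a last on-treatment, Early Termination or follow-up value from those who stop. They may overstate long-term response if non-responders stop more often, but neither size nor direction can be established from the documents. The tabulated gaps rest entirely on assumed stopping and response rates, and the gap vanishes if stoppers respond like stayers. Only a table that uses the stoppers' data can show which case applies.

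The plan already recognizes the value of showing both views, since TP1 PGI-C has both and only the observed one is carried forward. SAP 8.3 and Appendix 1 conflict on whether Observation Period values feed TP3 visits, and this needs correcting in any event. Overall this is an inexpensive improvement to descriptive endpoints.

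**What to change.** 1. Keep the observed-case tables for TP2 and TP3 and label them on-treatment.
2. For CSR 1 and CSR 2, add a supplementary PGI-C response table over all participants who entered the period. Count permanent stoppers as non-responders. Handle exits for commercial availability or sponsor closure separately, not as failures. Use one pooled group in CSR 2, as SAP 8.3 does.
3. Add a SALT summary that includes Observation Period values. Overall SALT is the natural choice, because the Observation Period list does not name the non-AA score from which AA SALT is derived.
4. At each visit print the numbers on drug, off drug, administratively exited and missing.
5. Reconcile SAP 8.3 with Appendix 1 on whether Observation Period data enter TP3 analysis visits.

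The cost is two supplementary tables, one row block of counts and an SAP edit. No new data are collected. The downside is that counting stoppers as non-responders is conservative, so that table should sit beside the observed-case one and not replace it.

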## 6. ANALYSES AND SUMMARIES

### 6.1. Primary Endpoint

- Primary endpoint: Change from baseline in I-V interwave latency on BAEP at a stimulus intensity of 80 decibels (dB) at Month 9;
- Population: Safety;
- Statistical Method: a linear mixed-effects model in Section 5.2, which includes all the post-baseline measurements through Month 9, will be used. The estimated means, with standard errors and 95% confidence intervals for each treatment group based on the model will be presented. Descriptive statistics will also be provided based on the observed data. Data from right side and left side will be summarized separately.

